# 2.4.2 Anticoagulation medications

The number and percentage of subjects treated with anticoagulation medications will be summarized prior to APT procedure, post procedure until discharge, at 3-month and 12-month follow-up.

#### 2.5 Efficacy outcome measures

Efficacy analyses will be performed for both the SP and EP populations. In addition to the analyses described below, efficacy outcome measures will also be summarized by the subgroups described in section 2.2.1. All observed data will be summarized without imputation for missing values.

Efficacy outcomes measured by echocardiogram including RV/LV, TAPSE, IVC Collapse, estimated RVSP and pulmonary arterial pressure will be summarized using descriptive statistics and 95% confidence intervals at each time point and/or study visit including change from baseline for continuous endpoints and shift tables for categorical variables.

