### 5.3 Outcome Measures

---

1. Change in the ratio of the measurement of the RV/LV diameters as measured by echocardiogram or CTA from baseline to between 24 – 48 hours after the start of the APT procedure (matched pairs as available).
2. Diagnosis of pulmonary hypertension defined as mean pulmonary artery pressure greater than 25 mm Hg by echocardiogram that persists at least 3 months after PE diagnosis
3. Frequency and safety outcomes of adjunctive therapies post APT procedure during hospitalization
4. Number of patients with non or partial response to other interventional procedures prior to APT procedure for index PE
5. Frequency and severity of SAEs related to EKOS and procedure, major bleeding, or VTE during index hospitalization and during first 12 months post-APT procedure
6. All-cause mortality during first 12 months post-APT procedure
7. Recurrent symptomatic PE, PE related death, hemodynamic collapse at 30 days (composite measure)
8. Healthcare utilization during hospitalization:
  - a. Time from hospital admission to ICU discharge
  - b. Time from hospital admission to discharge
9. Quality of life (QOL) as measured by the PEmb-QOL and EQ-5D-5L at baseline and 3 month and 12 month post-hospitalization subject follow-up visits
10. IVC filter placement (measured by number of occurrences)

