### 6.2.1 Inclusion Criteria

---

Retrospective cases must meet all of the following inclusion criteria:

1. Treated with APT procedure between January 1, 2014 and one year prior to date of site activation
2. RV/LV  $\geq 1.0$  from diagnostic CTA or echocardiogram
3. PE symptom duration  $\leq 14$  days
4. Troponin elevation

Prospective subjects must meet all of the following inclusion criteria:

5. Male or female  $> 18$  years of age and  $\leq 80$  years of age
6. RV/LV  $\geq 1.0$  from diagnostic CTA or echocardiogram
7. PE symptom duration  $\leq 14$  days
8. Troponin elevation
9. Signed informed consent obtained from subject or legally authorized representative
10. Investigator has selected EKOS to treat patient with massive or submassive PE

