## **8. MEASUREMENTS – RETROSPECTIVE**

### **8.1 Screening/Baseline**

The following data will be collected for screening, as available. Record most recent assessments prior to beginning of APT procedure.

- Review and confirmation of eligibility to participate in the registry
- Demographic information, medical history, and clinical risk factors
- CTA to evaluate the anatomic location of PE and degree of RV enlargement (as part of the initial diagnosis of PE). The RV/LV ratio at end-diastole will be determined from this image.
- Echocardiogram to measure: RV/LV ratio, TAPSE, estimated RVSP, and the collapse of the IVC with respiration
- Laboratory tests
  - Hemoglobin (Hgb)
  - Hematocrit (Hct)
  - Platelet count
  - Bleeding Times: aPTT, PT, and INR
  - Biomarker measurements: Troponin (to confirm eligibility), BNP/NT-proBNP, lactate/lactic acid, and D-dimer
- Anticoagulation medications 72 hours leading up to the APT procedure

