### **8.3 Post-Procedure**

---

The following data will be collected as available:

- First set of vital signs after end of APT procedure
- Laboratory tests
  - Hemoglobin (Hgb)
  - Hematocrit (Hct)
  - Platelet count
  - Creatinine
  - Bleeding Times: aPTT, PT, and INR
  - Biomarker measurements: Troponin, BNP/NT-proBNP, lactate/lactic acid, and D-dimer
- Echocardiogram 24 – 48 hours after start of APT procedure: RV/LV ratio, TAPSE, estimated RVSP, and the collapse of the IVC with respiration
- CTA 24 – 48 hours after start of APT procedure: RV/LV ratio
- Vital signs once at same time each day of hospitalization through discharge
- Length of post-procedure hospitalization (date and time of hospital discharge)
- SAEs related to EKOS or procedure, bleeding events, or VTE events

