## **13. STATISTICAL CONSIDERATIONS**

### **13.1 Statistical Analysis**

The statistical analysis plan (SAP) will be a separate document finalized prior to data analysis. The SAP will be updated as required, in association with any protocol amendments. The plan will include detailed descriptions of analysis methods, tables, listings and figures and will describe statistical programming considerations.

For descriptive statistics, continuous data (e.g., age) will be summarized with n, mean, median, standard deviation, minimum and maximum and categorical data (e.g., gender) will be summarized with observed counts and percentages for each category.

Patients will be analyzed according to the APT treatment protocol they received (i.e. duration of treatment and dose, type of fluid received). Frequency of use of each of the APT treatment protocols before and after OPTALYSE PE results were made public will be summarized and compared using fisher's exact test.

Each outcome measure will be summarized for the full registry population as well as separately by the different APT treatment protocols, including 95% confidence intervals. Additionally, outcome measures will be summarized by the following subgroups: submassive and massive PE, each region, and by the retrospective and prospective portions of the registry.

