### **13.7 Efficacy Outcome Measures Analyses**

Descriptive statistics will be used to summarize efficacy outcome measures RV/LV, TAPSE, IVC Collapse, estimated RVSP and pulmonary arterial pressure by time point and/or study visit including change from baseline for continuous endpoints.

Each efficacy outcome measure will be summarized for the full registry population as well as separately by the different APT treatment protocols, including 95% confidence intervals. Additionally, efficacy outcome measures will be summarized by the following subgroups: submassive and massive PE, each region, and by the retrospective and prospective portions of the registry.

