#### 1.1.1 Data collection schedule and assessments - Prospective\*\*

Assessments will be performed per Investigator's SoC and collected according to the schedule below. Assessments marked with an asterisk (\*) pertain to an outcome measure or eligibility.

	Baseline	Procedure/Post Procedure	Foll	ow-up
Assessment	Day -1	Day 0 thru Discharge	3 Months (±14 Days) Post APT (Phone or Visit)	12 Months (±1 Month) Post APT (Phone or Visit)
Informed Consent	Χ*			
Demographics	Χ*			
Medical history, risk factors	Χ*			
Vital signs 	Χ*	Х		
Physical Examination	Х			
СТА	Χ*	X*  (if collected)		
sPESI	Х			
APT Procedure		Х		
Echocardiogram 	Х*	X  (if collected)	X* (if collected)	X* (if collected)
Quality of life surveys 		X*	X*	Χ*
Laboratory tests 	Xe	Х		
Biomarkers 	Χ*	Х		
Adverse/VTE/Bleeding Events		X*	X*	X*
Anticoagulation medications	Х	Х	Х	Х

1. Record heart rate, blood pressure, respiratory rate, oxygen saturation vital signs at admission, at start and end of treatment, and once at same time each day of hospitalization

2. Includes RV/LV ratio, TAPSE, estimated RVSP, and collapse of the inferior vena cava (IVC) with respiration. Echocardiograms collected throughout the follow up period will be slotted by months from index procedure for analysis.

3. Collect 24 – 48 hours after the start of the APT procedure

4. PEmb-QOL and EQ-5D-5L

5. Hemoglobin (Hgb), hematocrit (Hct), platelet count, creatinine, activated partial thromboplastin time (aPTT), partial thromboplastin time (PT), and international normalized ratio (INR)

6. Record if collected within 48 hours prior to the start of APT procedure

7. Troponin, brain natriuretic peptide (BNP)/NT-proBNP, lactate/lactic acid, and D-dimer

\*\* For the retrospective portion of the study, data will be collected as available for 12 months post- index treatment and where possible according to the schedule above.

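### SAP 2.5 summarises RV/LV change by echocardiogram only, although outcome measure 1 allows echocardiogram or CTA and CTA values are collected

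*SAP*

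**What the plan says.** **The outcome.** Protocol 5.3, item 1, defines the RV/LV change "as measured by echocardiogram or CTA from baseline to between" 24 and 48 h after APT starts, using matched pairs where they exist. The synopsis repeats it. Protocol 13.1 commits to reporting it: "Each outcome measure will be summarized for the full registry population", with 95% confidence intervals. Protocol 13.7 names no modality: "Descriptive statistics will be used to summarize efficacy outcome measures RV/LV, TAPSE, IVC Collapse, estimated RVSP and pulmonary arterial pressure".

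**The data.** The RV/LV entry criterion may be met "from diagnostic CTA or echocardiogram" (Protocol 6.2.1). For the baseline CTA, Protocol 8.1 and 10.1 both say "The RV/LV ratio at end-diastole will be determined from this image". After the procedure, Protocol 8.3 and 10.3 both list "CTA 24 – 48 hours after start of APT procedure: RV/LV ratio". An echocardiogram in the same period is listed beside it.

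**The planned analysis.** SAP 2.5 is the only efficacy analysis text in the SAP, and it reads "Efficacy outcomes measured by echocardiogram including RV/LV, TAPSE, IVC Collapse, estimated RVSP and pulmonary arterial pressure will be summarized using descriptive statistics", with 95% confidence intervals and change from baseline. CTA appears in the SAP only as something collected (1.1 and 1.1.1). In the 1.1.1 schedule an asterisk marks assessments tied to an outcome or to eligibility. The post-procedure CTA carries it and the post-procedure echocardiogram does not.

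**Timing.** Note 3 to the SAP 1.1.1 schedule, attached to both post-procedure scans, says "Collect 24 – 48 hours after the start of the APT procedure". SAP 2.1 confines its windowing to follow-up assessments. It gives windows for the quality-of-life surveys, places echocardiograms in monthly slots, and picks the assessment nearest the middle when several share a window.

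**The concern.** The protocol defines the outcome over two imaging modalities and collects both. The SAP then plans an estimate from one of them. A programmer who follows SAP 2.5 would leave CTA readings out of the n, the mean change and the confidence interval for the first-listed outcome measure, and out of every subgroup summary built on it.

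Imaging here follows local standard of care, and the post-procedure scans are recorded only if done. The patients who remain in an echocardiogram-only summary are therefore selected by which scan each site happened to use. That is not the population the protocol describes, and the reader of the table would not see the difference.

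A lesser issue is timing. The SAP states the 24–48 h period as an instruction for collection and does not carry it into the analysis rules for choosing the reading.

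**Working it through.** No sample size, power or error rate is involved and the plan states no figure to reproduce. The check is a comparison of texts plus one short calculation.

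**Step 1. Modality, side by side.**

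| Place | RV/LV modality |
|---|---|
| Protocol 5.3, outcome 1 | Echocardiogram or CTA |
| Protocol 6.2.1, entry | CTA or echocardiogram |
| Protocol 8.1, 10.1, baseline | Both collected |
| Protocol 8.3, 10.3, 24–48 h | Both collected |
| Protocol 13.7, analysis | None named |
| SAP 1.1.1, schedule | Both; asterisk on the post-procedure CTA only |
| SAP 2.5, analysis | Echocardiogram only |

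The restriction enters at SAP 2.5 and nowhere else.

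**Step 2. Who is left out.** Take a patient whose RV/LV values at baseline and at 24–48 h are on CTA only. There is no echocardiographic value to summarise, so SAP 2.5 cannot include the patient on any reading. SAP 2.1 lists all eCRF data, so the values are listed but not estimated from.

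A patient with CTA at baseline and echocardiogram at 24–48 h is unclear. SAP 2.1 takes the last available value before APT as baseline and does not restrict its modality, and the protocol does not say whether *matched* means the same patient or also the same modality. Such a patient might or might not be counted. A full split of imaging patterns into included and excluded would need a pairing rule that neither document gives.

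**Step 3. Size.** The number lost is the number of patients with RV/LV on CTA only. Neither document gives the share scanned by each modality at either time, so this cannot be computed.

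**Step 4. Timing.** Note 3 fixes the period for both scans, and Protocol 8.3 and 10.3 treat them as distinct assessments. What is missing is the link: SAP 2.1 addresses follow-up assessments, and a monthly slot cannot isolate a 24–48 h reading. If the nearest-to-middle rule were applied to the period in note 3, the target would be (24 + 48)/2 = 36 h.

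**Step 5. Bedside echocardiograms.** At select sites, Protocol 11.9 adds hourly RV/LV readings from the start of APT until 4 h after it ends. For an APT duration of D hours the last reading is at about D + 4 h.

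- D = 2, 4 and 6 h (durations named in Protocol 13.6): 6, 8 and 10 h, all before 24 h.
- D + 4 ≥ 24 gives D ≥ 20 h: readings can then fall inside the period.
- Protocol 13.6 also has a category above 6 h and an open one, neither with an upper limit on duration. Protocol 4.3 describes earlier use averaging 18 h (18 + 4 = 22 h, outside) and an early study of about 25 h (25 + 4 = 29 h, inside).

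Most bedside readings would fall before the period, but for long procedures some could fall within it, so a time window alone does not settle their eligibility.

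**The case against.** The case for leaving the SAP alone has four parts.

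- **The protocol still governs.** Sections 13.1 and 13.7 promise the summary without limiting modality, the table shells are in a separate document, and CTA values are listed. This lowers the risk. It does not correct the SAP text, which is what a programmer would follow.
- **Version lag.** The SAP is based on protocol version 2.0 of 09 May 2018, while the protocol supplied cites a July 2018 publication and so appears later. That might explain the wording, but the SAP's own schedule already marks the post-procedure CTA, so the inconsistency is also internal to the SAP.
- **Timing is covered.** A reader might infer that the SAP has no 24–48 h period and no selection rule at all, leaving the choice of reading wholly open. The documents do not support that: note 3 gives the period for both scans, the protocol defines them as discrete assessments, and SAP 2.1 has a nearest-to-middle rule. This part of the objection largely stands. Only the missing link remains.
- **The consequence depends on pairing.** A reader might infer that only patients with an echocardiogram at both times enter the summary. Because SAP 2.1 sets no modality for baseline, that is one interpretation. The objection stands for mixed pairs and fails for patients with CTA only.

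Nor do the documents support an inference that bedside readings are planned to be pooled into outcome 1. Their eligibility is simply unstated.

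**Conclusion.** The mismatch is real and should be fixed. Outcome measure 1 admits CTA, CTA RV/LV is collected at both times in both portions, and the only planned estimate excludes it. Patients with RV/LV on CTA only would be listed and not summarised. Their number is unknown.

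The consequence is confined to a descriptive mean change and its 95% CI, overall and by subgroup. The outcome is not designated primary, and no hypothesis test or sample size rests on it.

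The conclusion assumes that SAP 2.5 is applied literally and that the unseen table shells do not already add CTA. The timing point is a secondary clarification.

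**What to change.** **SAP 2.5.** Add RV/LV change by CTA alongside echocardiogram, and report n, mean change and 95% CI for each modality. State how pairs that mix modalities are handled. At minimum, report how many there are, since *matched* is not defined. If a combined estimate is also shown, count each patient once by a prespecified order of modality.

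**SAP 2.1.** Link note 3 of the 1.1.1 schedule to the existing nearest-to-middle rule for the post-procedure reading. State whether Protocol 11.9 bedside echocardiograms may supply that reading when they fall inside 24–48 h.

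**Cost.** SAP wording and a few extra tables; CTA RV/LV is already among the data to be collected. Reporting by modality gives a smaller n in each table. If mixed pairs are only counted, those patients contribute to no mean change, which is a choice the SAP should make openly. The documents do not say whether scan clock times are captured. If they are not, the window has to rest on the site's assignment of the scan to the 24–48 h assessment.

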#### 2.6 Additional outcome measures

Analyses of additional outcome measures will be performed for both the SP and EP populations. In addition to the analyses described below, additional outcome measures will also be summarized by the subgroups described in section 2.2.1. All observed data will be summarized without imputation for missing values.

#### 2.6.1 Healthcare Utilization

Time from hospital admission to ICU and time from hospital admission to discharge will be summarized using descriptive statistics.

#### 2.6.2 Quality of Life Assessments

For the prospective portion of the study, PEmb-QOL and EQ-5D-5L will be summarized using descriptive statistics (N, mean, standard deviation, median, minimum, maximum) and 95% confidence intervals at each time point and/or study visit including change from baseline for continuous endpoints and observed counts, percentages and shift tables for categorical variables.

The PEmb-QOL questionnaire score ranges from 0 to 100. To score: Q1, Q4, Q5, and Q9 are to be reversedly scored with a low score indicating a better quality of life. Two questions (Q2 'At what time of day are your lung symptoms most intense?' and Q3 'Compared to one year ago, how would you rate the condition of your lungs in general now?') are not used for scoring. Item 4a will be considered missing if the answer was 'I do not work'. For a PEmb-QoL summary score, first transform each answered item score to a scale ranging from 0 to 100 (38 items total). Then average these transformed scores (except items Q2 and Q3) to obtain an overall summary score. No minimum is specified for the number of answered items.

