## 11.8 Quality of Life Assessments: PEmb-QoL and EQ-5D-5L

Two Quality of Life instruments, PEmb-QOL and EQ-5D-5L, will be used in this registry and are validated, widely used quality of life assessments.

The PEmb-QOL quantifies health-related quality of life after experiencing PE. This questionnaire consists of 10 questions for six health dimensions: frequency of complaints, activities of daily living limitation, work-related problems, social limitations, intensity of complaints, and emotional complaints.

The EQ-5D-5L is a patient reported outcome that provides a simple descriptive profile and single index value for health status. The questionnaire consists of 5 questions pertaining to specific health dimensions, including mobility, self-care, usual activities, pain/discomfort, anxiety/depression, and overall health status rating scale.

Subjects' responses to the questionnaires are to be recorded and entered into the EDC system.

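### The PEmb-QoL summary score may rest on any number of answered items, so a nearly empty form counts the same as a complete one

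*SAP*

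**What the plan says.** Quality of life is outcome 9. Protocol 5.3 defines it as "Quality of life (QOL) as measured by the PEmb-QOL and EQ-5D-5L at baseline and 3 month and 12 month post-hospitalization subject follow-up visits". Protocol 11.8 describes the PEmb-QoL as "10 questions for six health dimensions".

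The scoring rule is in SAP 2.6.2. Each answered item is rescaled to run from 0 to 100, with a total of 38 items mentioned. The SAP continues: "Then average these transformed scores (except items Q2 and Q3) to obtain an overall summary score". It then says: "No minimum is specified for the number of answered items". The only rule for a single item concerns 4a, which is set to missing for people who do not work.

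On missing data in general, SAP 2.6 says: "All observed data will be summarized without imputation for missing values". Protocol 13.11 says the same.

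On the analysis, SAP 2.6.2 says: "PEmb-QOL and EQ-5D-5L will be summarized using descriptive statistics (N, mean, standard deviation, median, minimum, maximum) and 95% confidence intervals". This applies at each time point in the prospective portion, with change from baseline. SAP 2.6 adds the subgroups of SAP 2.2.1: dose band, submassive or massive PE, region, and portion of the registry.

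No threshold, weight, flag or sensitivity analysis for incomplete PEmb-QoL forms appears in Protocol 11.8, 13.8 or 13.11, in SAP 2.1 or 2.6, or in the SAP appendix.

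**The concern.** A programmer who follows SAP 2.6.2 would score a form with one answer. That answer has weight 1/38 (2.6%) in a complete form and 100% when it stands alone, yet each patient counts once in N, mean, SD and confidence interval. The no-imputation wording does not prevent this, because averaging only the answered items lets them stand in for all the blank ones.

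Two consequences follow. A score meant to span six dimensions may reflect one of them. And if a patient answers different items at two visits, part of the apparent change comes from the change of items. The second objective is to describe long-term outcomes under varied APT protocols, and this is one of two patient-reported measures that reach 12 months. It is also to be broken down by five dose bands, where some cells may be small.

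**Working it through.** The documents give no sample size, power or precision figure for this outcome, so there is nothing to reproduce. The check asks how far a partial score can lie from the score the same patient would have had on a complete form.

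**Inputs**
- Number of items K = 38 (SAP 2.6.2). The SAP does not say whether this is before or after Q2 and Q3 are removed, so K = 36 is tried as well.
- Item SD s = 25 points on the 0 to 100 scale: assumed, not in the documents.
- Inter-item correlation r = 0.3 to 0.5: assumed, not in the documents.
- Items missing at random, with equal SDs and one common correlation: assumed.

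**Formulas**
- SD of the full score = s × √[(1 + (K − 1)r)/K].
- SD of the gap between a k-item score and the full score = s × √[(1 − r)(1/k − 1/K)].

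**Full score.** At r = 0.3: 25 × √(12.1/38) = 14.1. At r = 0.5: 25 × √(19.5/38) = 17.9.

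**Gap, in points**

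| Items answered (k) | 1/k − 1/38 | r = 0.3 | r = 0.5 |
|---|---|---|---|
| 1 | 0.9737 | 20.6 | 17.4 |
| 5 | 0.1737 | 8.7 | 7.4 |
| 19 | 0.0263 | 3.4 | 2.9 |
| 37 (only 4a missing) | 0.00071 | 0.6 | 0.5 |

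With K = 36 the figures move by about 0.1 point or less. At half the items (k = 18), for example, the gap is 25 × √(0.7 × 0.0278) = 3.5 at r = 0.3. With a wider assumption (s = 30, r = 0.3 to 0.7) the gap is about 16 to 25 points for one item, 7 to 10.5 for five and 3 to 4 for 19.

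**Change.** If one visit has a complete form and the other has five items, the whole 7 to 9 point gap passes into that patient's change.

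**Effect on the reported mean.** These are per-patient errors. Under the same assumptions the gap is uncorrelated with the full score, so the variances add. Suppose, for illustration, that 5% of forms are partial:
- Five items, r = 0.3: √(14.1² + 0.05 × 8.7²) = 14.2, so the standard error widens by about 1%.
- One item, r = 0.3: √(14.1² + 0.05 × 20.6²) = 14.8, about 5% wider.
- One item, r = 0.5: √(17.9² + 0.05 × 17.4²) = 18.3, about 2% wider.

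**Small cells.** In a cell of 10 patients, one five-item form moves the mean by an SD of 7.4/10 to 8.7/10, or 0.7 to 0.9 point. One one-item form moves it by 17.4/10 to 20.6/10, or 1.7 to 2.1 points. For comparison, the standard error of a 10-patient mean is 14.1/√10 = 4.5 to 17.9/√10 = 5.7 points.

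**Bias.** If items are not missing at random, and partial forms are off by d points on average, the mean shifts by the share of partial forms times d. At 5% that is one twentieth of d. Neither quantity is in the documents.

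**The case against.** The best defence is that the rule is disclosed and fits the plan's general principle of summarising all observed data. Setting partial forms to missing discards observed answers and needs a stated exception to that principle. This stands, and the fix allows for it.

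The sentence about no minimum is also passive. It may report the instrument's published scoring rather than a choice by the sponsor; the SAP's reference list includes a paper from a quality-of-life journal. That is possible, and the documents do not settle it. The effect on the analysis is the same either way.

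There is some mitigation. SAP 2.1 lists all eCRF data and derived variables, so incomplete forms can be found, and Protocol 15.11 allows queries on missing data. Neither keeps a nearly empty form out of the summary, and a query may not recover an answer the patient skipped.

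The stakes are low: one of ten outcomes, prospective portion only, descriptive, with no test or sample size resting on it.

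Three stronger readings are tempting and are not supported:
- A reader might infer that the sickest patients return the partial forms, so that results are biased in a known direction. Neither document says who leaves items blank, and the calculation assumes random missingness, so it says nothing about direction.
- A reader might take the 4a rule as evidence of damage. It is a sensible not-applicable rule, and one lost item moves the score by only about 0.5 to 0.6 point.
- A reader might treat the one-item figures as typical. They are the extreme case, and nothing shows that such forms will occur.

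**Conclusion.** The point holds as a modest improvement to the plan. As written, a form with few answers is scored and counted like a complete one, and change can compare different item sets. For an individual patient the error is material when few items are answered, and small (about 3 points) once half are. All these sizes rest on the assumed item SD and correlation and on random missingness.

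The size of the effect on the registry's results is unknown, because the rate of partial forms is not given. If a few per cent of forms are partial, the standard error widens by about 1 to 5% and the overall means and intervals barely change. A reader might infer that the PEmb-QoL results as a whole are unreliable; the documents do not support that. The main exposure is small subgroup cells and individual change scores.

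**What to change.** Amend SAP 2.6.2 before the analysis:
1. State the number of scored items after Q2 and Q3 are removed, since the total of 38 can be read either way.
2. Compute the summary score only when at least half of the applicable scored items are answered (19 if 38 are scored, 18 if 36). Do not count 4a for people who do not work. Otherwise set the score to missing.
3. State this as an exception to the all-observed-data wording in SAP 2.6, which Protocol 13.11 shares.
4. Report the number of forms excluded at each visit.
5. Repeat the summary with all forms as a sensitivity analysis.

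If the present rule comes from the instrument's scoring source, say so, so that the departure is visible. Half is a convention; what matters is that a minimum is fixed in advance.

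The cost is a short paragraph, one count per visit and one repeated table. A few partial forms leave the main summary. The half rule limits differences in dimension coverage but does not remove them: two forms with 19 of 38 items each could still share none.
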